5.1.3 Day 8 (± 1 day) of Each Cycle

- Physical examination, including neurological examination and including whole body skin assessment. Whole body skin assessment does not have to be performed by a dermatologist; however, any unexplained lesion will be referred to a dermatologist for further evaluation and skin biopsy, if clinically warranted (Cycles 1 and 2). The examination must include a determination if the patient has had any infection. At the discretion of the investigator, evaluation of any reported infection must be conducted to rule out infection with a microorganism that may be associated with autoimmune or neurological disease(s) as specified in the exclusion criteria.
- Weight
- Vital signs.

- Hematology.
- Biochemistry.
- Urinalysis.
- Additional renal function studies.
- PK blood sample collection (Cycles 1 and 2).
- Sample collection and shipment for PBMC subset analysis (Cycles 1 and 2, for additional sample collections following dosing see [Appendix 13.1.2](#); only in Study Part 2).
- AEs.
- Concomitant medication use.

5.1.4 Day 15 (\pm 1 day)

- Physical examination, including neurological examination and including whole body skin assessment. Whole body skin assessment does not have to be performed by a dermatologist; however, any unexplained lesion will be referred to a dermatologist for further evaluation and skin biopsy, if clinically warranted (Cycles 1 and 2). The examination must include a determination if the patient has had any infection. At the discretion of the investigator, evaluation of any reported infection must be conducted to rule out infection with a microorganism that may be associated with autoimmune or neurological disease(s) as specified in the exclusion criteria.
- Weight
- Vital signs (Cycles 1 and 2).
- Hematology.
- Biochemistry.
- Urinalysis.
- Additional renal function studies.
- Sample collection for analysis of PK.
- Sample collection and shipment for PBMC subset analysis (Cycles 1 and 2, for additional sample collections following dosing see [Appendix 13.1.2](#); only in Study Part 2).
- AEs.
- Concomitant medication use.

5.1.5 End of Treatment Visit

The following procedures will be performed as soon as possible after decision to discontinue the study drug and prior to initiation of anticancer treatment:

- Serum or urine pregnancy test.
- Physical examination, including neurological examination and including whole body skin assessment. Whole body skin assessment does not have to be performed by a dermatologist; however, any unexplained lesion will be referred to a dermatologist for further evaluation and skin biopsy, if clinically warranted. The examination must include a determination if the patient has had any infection. At the discretion of the investigator, evaluation of any reported infection must be conducted to rule out infection with a microorganism that may be associated with autoimmune or neurological disease(s) as specified in the exclusion criteria.
- Vital sign measurements.
- ECOG performance status.
- Weight
- Disease assessments:
 - Patients who already have documented objective disease progression do not need to have assessments repeated.
 - Patients who do not already have documented objective disease progression will have assessments performed at the end of treatment visit if the most recent disease assessment was > 9 weeks prior to the end of treatment visit.
- Hematology.
- Coagulation panel.
- Biochemistry.
- Urinalysis.
- Additional renal function studies.
- 12-lead ECG.
- Sample collection for central laboratory assessment of PK, [REDACTED], ADA, and [REDACTED]
- Sample collection and shipment for PBMC subset analysis (only in Study Part 2).
- AE collection (collected until 84 days [12 weeks] after last dose of study drug).
- Concomitant medication use.

5.1.6 Long-term Follow-up

Patients who discontinue treatment for any reason other than objective disease progression will continue to be followed with scans approximately every 12 weeks from the last tumor assessment until disease progression, or initiation of new anticancer treatment. If a patient discontinues treatment for a hematopoietic stem cell transplant, the frequency of imaging will be as per the transplant center standard of care.

After documentation of disease progression or start of new anticancer treatment, patients will be contacted by telephone approximately every 12 weeks for up to 12 months after the last dose of study drug to collect survival information.

Blood Sample Collection and Adverse Event Monitoring During Long-Term Follow-up

For all patients, PK and ADA blood sample collection will be performed 12 weeks (\pm 1 week) following the last dose of ADCT-301, unless a new anticancer treatment has been initiated.

Patients who test positive for ADAs may be requested to supply additional ADA samples.

For all patients, collection of AEs and SAEs will continue for 12 weeks after the last dose of study drug or initiation of new anticancer treatment (see [Section 7.3.2.2](#)).

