4.1 Study Design

This is a Phase 1, FIH, open-label, dose-escalation (Part 1) and expansion (Part 2) study of ADCT-301 in patients with relapsed and refractory lymphoma. The study will evaluate the safety and tolerability of ADCT-301 as monotherapy, as well as the preliminary activity, PK, pharmacodynamics, and formation of ADAs of ADCT-301 in patients.

For each patient, the study will include a screening period (up to 28 days), a treatment period (until progressive disease, intolerable toxicity, or withdrawal of consent), and a follow-up period to assess disease progression and survival for up to 12 months after the last dose of study drug. The total study duration will be dependent on overall patient tolerability to the study drug and response to treatment. It is anticipated that the entire study (Parts 1 and 2) could last approximately 3 years from first patient treated to last patient completed.

In Part 1, patients will receive ADCT-301 administered as a 1-hour IV infusion on Day 1 of each 3-week (21-day) cycle. If ADCT-301 is well tolerated after the first cycle, the infusion duration may be shortened to 30 minutes for subsequent cycles at the Investigator's discretion.

The first patient at each dose level will be monitored for any AEs for 7 days before proceeding with dosing for the second patient.

The initial dose level for Part 1 will be 3 µg/kg (Dose Level 1). The highest allowed dose will be 300 µg/kg. The MTD will be the highest safe dose that has at least a 60% probability that the dose-limiting toxicity (DLT) rate is < 30%.

After discontinuation of treatment, patients without documented objective disease progression will be followed until progression of disease or initiation of new anticancer therapy for up to 12 months. All patients will be followed for survival (by telephone contact or retrospective chart review) until a new anticancer therapy is initiated or for up to 12 months after treatment discontinuation.

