11.3 Study Termination

The Sponsor has every intention of completing the study; however, the Sponsor reserves the right to discontinue the study at any time for clinical or administrative reasons.

The end of the study is defined as the date on which the last patient completes the last visit to the study site (includes any end of treatment visit to the site and any visit to the site to obtain confirmatory scan of response).

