### **4.9.5 Overall Survival**

Overall survival is defined as the interval between the date of first dose and the date of death from any cause. Patients who are known to be alive as of their last known status will be censored at their date of last contact. Patients who are lost to follow-up will be censored at the date the patient is last known to have been alive. The last confirmed alive date is the latest of the following: study visit date, telephone contact date, end of study last confirmed alive date, follow-up systemic (anticancer) therapy end date or start date (if ongoing or end date is missing), local or central radiologist scan date, or other date in the clinical database.

OS will be estimated and displayed by dose levels for the efficacy analysis set using Kaplan-Meier methods (SAS® PROC LIFETEST). A Kaplan-Meier plot will be presented.

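### Survival follow-up hangs on the last dose and, in Protocol 4.1, stops at new therapy, so Kaplan-Meier OS is likely inflated, chiefly in its tail

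*Protocol*

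**What the plan says.** - **Clock.** SAP 4.9.5: "Overall survival is defined as the interval between the date of first dose and the date of death from any cause". Protocol 8.6.1.3 agrees.
- **Time on drug.** Protocol 4.1 gives "a treatment period (until progressive disease, intolerable toxicity, or withdrawal of consent". There is no fixed number of cycles.
- **Length of survival follow-up.** Protocol 4.1 plans "a follow-up period to assess disease progression and survival for up to 12 months after the last dose of study drug". For those who have progressed or started another therapy, section 5.1.6 has this rule: "patients will be contacted by telephone approximately every 12 weeks for up to 12 months after the last dose of study drug". The Synopsis (Efficacy Assessments) and footnote 26 of the Schedule of Study Procedures repeat this.
- **A second, different rule.** Protocol 4.1 and the Synopsis (Study Design) also say that all patients are followed for survival "until a new anticancer therapy is initiated or for up to 12 months after treatment discontinuation".
- **Analysis.** SAP 4.9.5: "Patients who are known to be alive as of their last known status will be censored at their date of last contact", and "OS will be estimated and displayed by dose levels for the efficacy analysis set using Kaplan-Meier methods". The SAP gives no truncation point, sensitivity analysis or comment on informative censoring for OS. Unlike PFS and duration of response, OS is not censored at subsequent therapy, and the list of last-alive sources includes dates of follow-up systemic therapy.

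**The concern.** Kaplan-Meier needs patients censored at time t to have the same later death risk as those still followed. Here the latest planned contact is set by the last dose, while the OS clock starts at the first. After month 12 the risk set therefore keeps those who stayed on drug and drops early stoppers who are still alive. Progression ends treatment, so early stoppers plausibly have the worse outlook.

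The second rule acts sooner. If contact ends when a patient starts new therapy, patients who have come off drug leave the risk set selectively from the first months.

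At stake are the OS rates and curves by dose level, a named secondary objective. Time on drug may differ between dose levels, and the length of follow-up would then differ with it.

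**Working it through.** The documents give no OS rate, median or event count, so there is no plan figure to reproduce.

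**1. Who is observable (from the documents).** Let D be the time from first to last dose. Under 5.1.6 OS is censored no later than D + 12 months, so a patient can be seen at month t > 12 only if D ≥ t − 12. On schedule, cycle k is given 21 × (k − 1) days after the first dose; one month is 30.44 days.

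| Month t | Last dose needed at or after | First qualifying cycle |
|---|---|---|
| 13 | month 1 (30 days) | 3 (day 42) |
| 15 | month 3 (91 days) | 6 (day 105) |
| 18 | month 6 (183 days) | 10 (day 189) |
| 24 | month 12 (365 days) | 19 (day 378) |

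**2. Size under the 5.1.6 rule (assumed inputs).** OS = D + Y, where Y is survival after the last dose. D and Y are exponential, with a shared gamma frailty of mean 1 and variance v multiplying both hazards; 400,000 simulated patients per scenario. Base case: median D 3 months and median Y 9 months before frailty, v = 0.5.

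| Month | True OS | Kaplan-Meier | Difference | Living patients still observed | At risk per 10 |
|---|---|---|---|---|---|
| 12 | 61.4% | 61.4% | 0 | 100% | 6.1 |
| 15 | 53.6% | 54.4% | +0.8 | 73% | 3.9 |
| 18 | 47.1% | 49.5% | +2.4 | 57% | 2.7 |
| 24 | 37.0% | 43.0% | +6.0 | 40% | 1.5 |

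- Range over median D 1.5 to 3, median Y 6 to 15 and v 0 to 1: 0 to +1.5 points at month 15, about 0 to +4.1 at month 18, about 0 to +9.5 at month 24.
- With v = 0 (survival after the drug unrelated to time on it): at most +0.7 at month 18 and +1.4 at month 24.
- A different assumed population: 60% with median 1.4 months on drug then 6 months' survival, 40% with 6 then 20. Result: about 41.6% against 38.3% at month 18, and 35.6% against 28.8% at month 24.
- Median OS: 17.6 months against a true 16.6 in the base case, and 13.1 against 13.0 in the 60/40 population. A later median can move more: with median D 1.5, median Y 9 and v = 1 it is 21.8 against 16.9.
- Transplant: if 20% stop within 1 to 3 months and then have median survival of 48 months, the bias at months 18 and 24 is −2.3 and −4.9 points with v = 0, but +1.0 and +3.3 with v = 0.5.

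**3. Last call before month 12.** Calls every 12 weeks fall at weeks 12, 24, 36 and 48; the next, week 60, is past 12 months. Week 48 is 336 / 30.44 = 11.0 months. If it is the last contact, the base-case bias is +0.1 at month 12, +3.3 at month 18 and +7.3 at month 24.

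**4. Size under the 4.1 rule.** Base case, with an assumed share starting new therapy at a median of 1.5 months after the last dose:
- 30%: month 12 shows 64.5% against 61.4% (+3.1).
- 50%: month 12 shows 67.3% against 61.3% (+6.0). The bias is already +2.9 at month 6, reaches +9.9 at month 18, and the median is about 26 months against 16.5.
- In the 60/40 population, with 30% to 50% starting at a median of 1.5 to 2 months: +2.6 to +5.6 at month 12.

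**5. Common cut-off.** Base case, everyone followed to one calendar date (assumed 12 to 36 months of potential follow-up): 47.0% against 47.0% at month 18 and 36.9% against 36.9% at month 24, within 0.1 point throughout.

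**The case against.** The direction of the bias is assumed. No document gives survival by time on drug, Protocol 5.2.1 lists many reasons for stopping besides progression, and 5.1.6 itself foresees stopping for transplant. This stands: upward is the likely direction, not a proven one.

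Sampling error exceeds the bias. In the 60/40 population the standard deviation of the Kaplan-Meier estimate at month 18 is about 17 points for a cohort of 10 and 4.7 for all 140 patients, against a bias of a little over 3. This also stands, and it argues for numbers at risk. But a confidence interval does not correct a systematic error, and the bias does not shrink when dose levels are pooled.

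Nothing is tested (SAP section 4), no dose decision uses OS, and the loss is gradual: in the base case 89% of living patients are still observed at month 13. All true, and this limits the point to a cheap improvement.

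The SAP's list of last-alive sources may pick up later dates for some patients. It does not plan later contact, and what it finds depends on who happens to have data.

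**Conclusion.** The point holds. From the documents alone: after month 12, planned OS observation depends on time on drug, the SAP has no safeguard, and Protocol 4.1 contradicts 5.1.6 on whether survival follow-up outlasts new therapy. The size rests on the assumed survival models above: about 0 to +4 points at month 18 and about 0 to +9.5 at month 24 under 5.1.6, and about +3 to +6 points already at month 12 under the 4.1 rule. Under 5.1.6 the median is little affected if it falls in the first 16 months or so; a later one lies in the affected part of the curve.

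Three stronger readings are tempting and not supported:
- **The curve is certainly biased upward.** Bias is near zero if death risk is unrelated to time on drug, and can be negative with many early transplants.
- **OS up to month 12 is sound as planned.** This holds only if 5.1.6 governs and vital status is confirmed at or after month 12; the 4.1 rule and a last call at week 48 both break it.
- **Protocol 11.3 adds to the bias.** It says "The end of the study is defined as the date on which the last patient completes the last visit to the study site". That is a calendar limit for everyone, which is administrative censoring and a separate matter from censoring by time on drug.

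**What to change.** 1. Reconcile Protocol 4.1 and the Synopsis (Study Design) with 5.1.6, so that survival follow-up continues after new anticancer therapy. The OS definition in SAP 4.9.5 already presumes this.
2. Make one vital-status check, by call or chart review, of every patient not known to have died, at one common calendar cut-off, including those whose 12 months have run out. In SAP 4.9.5, count deaths up to that date and censor survivors there; anyone not traced is censored when last known alive.
3. If that check is not made, confirm vital status at or after month 12 from first dose for every patient, limit OS estimates to 12 months, and print numbers at risk under each curve. Truncating at month 12 without step 1 is not enough.

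Cost: a wording change in the protocol and SAP, plus one contact or chart check per survivor. Under step 3 the price is no OS estimate beyond 12 months. Sample size and the dose-escalation rules are untouched.

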5.2 Withdrawal of Patients from the Study

The duration of the study participation for each patient is defined as the time from the date of signed written informed consent through the completion of the follow-up period or withdrawal of consent.

5.2.1 Reasons for Withdrawal/Discontinuation

Patients may withdraw from treatment at any time and for any reason without prejudice to their future medical care by the Investigator or others at the study site. A patient may be withdrawn from treatment for any of the following reasons:

- Objective disease progression.
- Clinical progression.
- AE.
- Withdrawal of consent.
- Major protocol deviation.
- Required treatment delay > 21 days (except in case of potential patient benefit, which must be approved by the Sponsor).
- Non-compliance, including lost to follow-up.
- Pregnancy

- Other (e.g., development of contraindications with use of the study drug).
- The Investigator determines if it is in the best interest of the patient to discontinue the patient's participation in the study.
- Discontinuation of the study by the Sponsor.
- Death.

5.2.2 Handling of Withdrawals

Upon occurrence of a serious or intolerable AE, the Investigator will confer with the Sponsor. If a patient discontinues because of an AE, then the event will be followed until it is resolved. When a patient withdraws from the study, the reason(s) for withdrawal shall be recorded by the Investigator on the relevant page of the electronic case report form (eCRF). Whenever possible, all patients who discontinue study treatment or withdraw from the study prematurely will undergo all end of treatment assessments. Patients who fail to return for final assessments will be contacted by the site. Following a minimum of two documented unsuccessful telephone calls, a registered letter will be sent to the patient in a final attempt to ensure protocol compliance.

5.2.3 Patient Replacements

Patients in Part 1 who discontinue treatment for any reason without a DLT AE before completion of the first treatment cycle will be replaced. No other patients will be replaced.

6 Study Treatments

6.1 Method of Assigning Patients to Treatment Groups

This is an open-label study that will be conducted in 2 parts. In both parts, ADCT-301 will be administered on Day 1 of each cycle. The duration of each cycle will be 21 days (3 weeks).

In Part 1, dose escalation will begin with the 3 µg/kg dose starting dose (Dose Level 1). The maximum dose will be 300 µg/kg. Patients will be assigned to the appropriate dose level according to the CRM design ([Section 13.5](#)) and judgment of the DESC.

In expansion (Part 2), all patients will be assigned to the dose level of ADCT-301 as identified in Part 1 by the DESC.

6.2 Prophylactic Treatments for Hypersensitivity

If Grade 2 or higher infusion-related hypersensitivity reactions are observed in a patient at any time during the study, this patient must receive prophylactic treatment with all subsequent dosing, as described below or as per the institution's standard of care, to reduce the risk of hypersensitivity reactions:

- Patient will be instructed to take 20 mg of dexamethasone orally at 12 hours and 6 hours before the start of ADCT-301 infusion on Day 1 of each cycle. When necessary, 12 and 6 hours before the first infusion may be defined as “immediately before sleeping” and “immediately after waking up.”
- Patient will be given 50 mg of diphenhydramine hydrochloride intravenously 30 minutes before the start of the ADCT-301 infusion on Day 1 of each cycle.
- Patient will be given 50 mg of ranitidine intravenously 30 minutes before the start of ADCT-301 infusion on Day 1 of each cycle.
- For 2 days after administration of ADCT-301, dexamethasone 4 mg (twice per day) will be taken orally by the patient.

Other doses and other medications for prophylaxis and treatment of hypersensitivity or infusion reactions may be administered according to standard treatment center protocols. Medications for the treatment of severe hypersensitivity reactions including anaphylaxis should be available for immediate use.

If a Grade 1 or Grade 2 hypersensitivity occurs in a patient, the following medications should be administered for 48 hours after ADCT-301 infusion:

- Ranitidine 150 mg orally given 2 times per day
- Diphenhydramine hydrochloride 50 mg orally given 3 times per day

If a Grade 3 or higher hypersensitivity occurs, the patient should be discontinued from the study and must be treated immediately with hydrocortisone 20 mg administered intravenously and/or other appropriate medications. In case of life-threatening symptoms (e.g., arrhythmia, hypotension, respiratory distress, seizures, shock, stridor, unconsciousness, wheezing), epinephrine 0.2 to 0.5 mL of 1:1000 dilution should be administered subcutaneously or intramuscularly, repeating every 5 minutes to a total dose of 1 mg. In these cases, patients must be carefully observed after the treatment. Additional therapy per institution standard of care should also be followed.

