6.4 Dose Delays and Modifications

The Investigator may suspend ADCT-301 dosing for up to 21 days for any patient who experiences a protocol-defined DLT during any treatment cycle.

At the discretion of the Investigator, the dose may also be delayed for up to 21 days for any other toxicity of any grade.

Resumption of dosing with ADCT-301 after any suspension, even when longer than 21 days, is at the discretion of the Investigator, in consultation with the Sponsor, based on assessment of the patient's clinical condition and whether or not the patient is deriving potential clinical benefit from treatment with ADCT-301. Following recovery to Grade 1 or baseline, treatment may resume at the Investigator's discretion.

Patients who resume treatment following a dose delay may, at the discretion of the Investigator, have their dose reduced by 1 dose level in either part of the study. If toxicity reoccurs at a severity that would mandate a dose delay, then the dose may be further reduced 1 dose level. If toxicity reoccurs at such level, then the patient is to be discontinued from treatment. Dose re-escalation is allowed at the investigator's discretion, at maximum to the dose level the patient was initially assigned to.

Patients experiencing certain types of infection during the course of participation in this clinical study also must delay further dosing, as stipulated in [Section 7.3.4.5](#).

Patients experiencing any autoimmune toxicities (e.g. endocrinopathies) \geq Grade 1 need to be followed at least weekly to quickly detect deterioration and modify dosing as per DLT criteria (can be done by telephone unless symptoms worsen).

Patients experiencing the following significant toxicities will be immediately and permanently withdrawn from treatment with ADCT-301:

- Any patient who experiences a Grade 3 or higher hypersensitivity reaction, regardless of premedication, during any cycle of treatment per CTCAE definitions ([Appendix 13.4](#)).
- Any patient who experiences a recurrent Grade 3 or 4 toxicity excluding hematological toxicity.
- Any patient who requires a dosing delay $>$ 21 consecutive days from the planned Day 1 dosing at any time during treatment (except in case of potential patient benefit, which must be approved by the Sponsor).

Neurological toxicities: dose delay/permanent discontinuation

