7.3.2.2 Eliciting and Documenting Adverse Events

All AEs will be assessed from the time the patient signs the ICF until 84 days (12 weeks) after the last dose of study drug, or initiation of new anticancer treatment.

Any SAEs that occur > 84 days (12 weeks) after the last dose of study drug do not need to be reported unless the Investigator considers the event to be related to study drug.

At every study visit, patients will be asked a standard non-leading question to elicit any medically related changes in their well-being. They will also be asked if they have been hospitalized, had any accidents, used any new medications, or changed concomitant medication regimens (both prescription and over-the-counter medications).

In addition to patient observations, AEs will be documented from any data collected on the AE page of the eCRF (e.g., clinically significant changes in laboratory values, physical examination, ECG changes, etc.) or identified from review of other documents that are relevant to patient safety.

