### 4.3 Protocol Deviations

The number and percentage of patients with any important clinical study report (CSR) reportable protocol deviation will be summarized overall and by type of deviation. The pre-defined important CSR reportable protocol deviations are listed below; in addition, any other protocol deviations deemed by ADCT medical to be important CSR reportable deviations will be included in the summary.

1. Patient entered the study even though they did not satisfy the entry criteria
2. Patient received a prohibited concomitant treatment during the study
3. Patients who met criteria for mandatory withdrawal of study drug during the study but did not have study drug withdrawn. The criteria for mandatory withdrawal of study drug included:
  - Any patient who experiences a Grade 3 or higher hypersensitivity (Appendix 13.4 in the protocol) reaction, regardless of premedication, during any cycle of treatment.
  - Any patient who experiences a recurrent Grade 3 or 4 toxicity, excluding hematological toxicity.
  - Any patient who requires a dosing delay >21 consecutive days from the planned Day 1 dosing at any time during treatment (except in case of potential patient benefit, which must be approved by the Sponsor).
4. Patient who received the wrong treatment or incorrect dose. For example,
  - Actual dose of study drug was more than 15% greater than protocol defined planned dose level.
  - Patient started next cycle less than 18 days later after Day 1 of the most recent treatment cycle.

Important protocol deviations will be listed.

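### Protocol 6.2 takes a patient with Grade 3 or higher hypersensitivity off the study, while 6.4 and SAP 4.3 withdraw ADCT-301 and 5.1.6 and 4.1 continue follow-up

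*Protocol*

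**What the plan says.** Three places give the consequence of a Grade 3 or higher hypersensitivity reaction:

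- Protocol 6.2: "If a Grade 3 or higher hypersensitivity occurs, the patient should be discontinued from the study and must be treated immediately".
- Protocol 6.4, whose list includes this reaction: "Patients experiencing the following significant toxicities will be immediately and permanently withdrawn from treatment with ADCT-301".
- SAP 4.3, which counts as an important deviation "Patients who met criteria for mandatory withdrawal of study drug during the study but did not have study drug withdrawn" and names the same reaction among the criteria.

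Other sections say what happens once dosing ends. Protocol 5.2 defines participation as running from consent "through the completion of the follow-up period or withdrawal of consent". Protocol 5.1.6 has three relevant rules:

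- Imaging: "Patients who discontinue treatment for any reason other than objective disease progression will continue to be followed with scans approximately every 12 weeks", until progression or new anticancer treatment.
- Survival, with a limit of 12 months from the final dose: "After documentation of disease progression or start of new anticancer treatment, patients will be contacted by telephone approximately every 12 weeks".
- Blood samples: "For all patients, PK and ADA blood sample collection will be performed 12 weeks" after the last dose, unless new anticancer treatment has started.

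Protocol 4.1 also provides for progression follow-up and for survival follow-up of all patients, the latter by telephone or retrospective chart review. Protocol 7.3.2.2 has adverse events assessed "until 84 days (12 weeks) after the last dose of study drug, or initiation of new anticancer treatment".

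**The concern.** Stopping a drug and leaving a study are different acts. The first triggers the off-treatment schedule; the second normally ends data collection. Section 6.2 orders the second for an event where the rest of the plan orders the first. It is also the section a site is likely to open while managing a severe reaction.

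At stake is follow-up in patients who have just had a serious drug toxicity. Overall survival, progression-free survival, duration of response, pharmacokinetics and anti-drug antibodies are all secondary objectives. A late antibody result is of obvious interest after a severe hypersensitivity reaction. A patient who leaves early would be censored at the last valid disease assessment for progression-free survival (SAP 4.9.4) and at the date last known alive for survival (SAP 4.9.5). The reason for that censoring would be the toxicity itself.

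**Working it through.** This is a question of wording, and the plan has no figure to reproduce. There are two steps: decide which clause is wrong, then trace what a literal reading of 6.2 would remove.

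**Which clause is wrong.** Protocol 6.4 and SAP 4.3 agree with each other and concern the drug. Under 5.2, participation ends at completion of follow-up or at withdrawal of consent; a toxicity is not an end point. Section 5.2 is a definition and does not itself order visits. The requirements are in 5.1.6 and 4.1, and neither makes an exception for hypersensitivity. Section 6.2 stands alone.

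**What a literal reading would remove.** The key text is protocol 5.2.2. It asks, whenever possible, for all End of Treatment assessments both in patients who stop study treatment and in those who leave the study early. Anything on the End of Treatment list in 5.1.5 is therefore largely safe; anything found only in the follow-up schedule is exposed.

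| Item | Where required | If 6.2 is followed literally |
|---|---|---|
| The reaction itself | 5.2.2, until resolved | Kept |
| Other adverse events to day 84 | 5.1.5 list; repeated for all patients in 5.1.6 and in the schedule of procedures (13.1.1, footnote 24) | Largely kept |
| PK and antibody sample at End of Treatment | 5.1.5 list | Kept whenever possible |
| PK and antibody sample at 12 weeks | 5.1.6, 7.2, follow-up columns of 13.1.1 and 13.1.2 | Could be omitted |
| Scans about every 12 weeks | 5.1.6 | Could be omitted |
| Survival contacts | 5.1.6, 4.1 | Could be omitted; chart review may recover status |

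**Size per affected patient.**

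- PK and antibody sampling: one time point.
- Scans and survival contacts: 52 weeks / 12 weeks = 4.3, so about four slots in 12 months. Each slot is a scan before progression or new treatment, or a telephone contact afterwards. They follow one another and should not be added together.

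These are upper limits. New anticancer treatment would end the scans and cancel the 12-week sample in any case.

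**Number of patients.** The documents give no incidence of Grade 3 or higher hypersensitivity, and none is assumed here.

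**The case against.** The strongest reply is that 6.2 is a slip that few would take literally. The protocol uses these terms loosely. Section 5.2 is headed as withdrawal from the study, yet 5.2.1 lists reasons for stopping treatment. Section 5.2.3 replaces patients who stop treatment, while the DLT-evaluable set in 8.4 excludes patients who leave the study. Section 6.2 concerns prophylaxis and is phrased as advice, whereas 6.4 governs dosing and is phrased as a requirement. Many sites would probably read 6.2 as applying to the drug alone.

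Most of that stands, and it is why the point is minor. It does not remove the conflict. No passage says that 6.2 means the drug only, 5.2.2 distinguishes the two kinds of withdrawal, and SAP 4.2 tabulates them separately.

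A reader might go the other way and infer that 6.2 cuts off most of the 84-day adverse event window and so biases the primary safety tables downward. The documents do not support this. Collection to day 84 is itself an item on the End of Treatment list, and 5.2.2 extends that list to patients who leave the study. The remaining weakness is only that 5.2.2 applies whenever possible.

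A reader might also infer that 6.2 removes patients from the efficacy analysis. A patient with no valid post-baseline assessment and no documented progression or death is indeed left out, but through the SAP 4.1.3 definition. The protocol's own set in 8.4 keeps patients who lack an assessment because of toxicity. That is a separate matter.

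**Conclusion.** The inconsistency is real and in current text, and 6.2 is the clause to change. Its reach is limited to the 12-week PK and antibody sample, the scans about every 12 weeks and the survival contacts, with survival status possibly recoverable from charts. This rests on a site following 6.2 literally, which is possible but not the likeliest reading. The number of patients affected is unknown and probably small.

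Dosing is not affected, because both clauses stop it. Nor is the dose-escalation input: the reaction is already a dose-limiting toxicity under 7.3.1.1. No effect on adverse event rates is claimed. Confidence in the mismatch of wording is high. Severity is minor.

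**What to change.** In protocol 6.2, replace the words that take the patient off the study with: *permanently withdrawn from treatment with ADCT-301 (Section 6.4) and followed per Sections 5.1.5–5.1.6 unless consent is withdrawn*. Tell sites of the change, so that any patient who has already had such a reaction stays in follow-up.

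The cost is one sentence in the next amendment and a note to sites. No dosing rule changes, and no visit or sample is added, because 5.1.5 and 5.1.6 already require them. The SAP needs no change on this point.
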